11.2. Audits and Inspections

Authorized representatives of the Sponsor, a regulatory authority, an Independent Ethics Committee or an Institutional Review Board may visit the site to perform audits or inspections, including source data verification. The purpose of audit or inspection by the Sponsor or its representative is to systematically and independently examine all study-related activities and documents to determine whether these activities were conducted, and data were recorded,

analyzed, and accurately reported according to the protocol, Good Clinical Practice guidelines of the International Conference on Harmonization, and any applicable regulatory requirements. The Investigator should contact the Sponsor immediately if contacted by a regulatory agency about an inspection.

12. QUALITY CONTROL AND QUALITY ASSURANCE

To ensure compliance with Good Clinical Practices and all applicable regulatory requirements, the Sponsor or its representative may conduct a quality assurance audit. Please see [Section 11.2](#) for more details regarding the audit process.

13. ETHICS

13.1. Ethics Review

The final study protocol, including the final version of the Informed Consent Form (ICF), must be approved or given a favorable opinion in writing by an IRB or IEC as appropriate. The Investigator must submit written approval to the Sponsor or its representative before he or she can enroll any subject into the study.

The Principal Investigator is responsible for informing the IRB or IEC of any amendment to the protocol in accordance with local requirements. In addition, the IRB or IEC must approve all advertising used to recruit patients/subjects for the study. The protocol must be re-approved by the IRB or IEC upon receipt of amendments and annually, as local regulations require.

The Principal Investigator is also responsible for providing the IRB with reports of any reportable serious adverse drug reactions from any other study conducted with the IP. The Sponsor or its representative will provide this information to the Principal Investigator.

Progress reports and notifications of serious adverse drug reactions will be provided to the IRB or IEC according to local regulations and guidelines.

13.2. Ethical Conduct of the Study

The study will be performed in accordance with ethical principles that have their origin in the Declaration of Helsinki and are consistent with ICH/Good Clinical Practice, applicable regulatory requirements and the Sponsor's policy on Bioethics.

13.3. Written Informed Consent

The Principal Investigator will ensure that the subject is given full and adequate oral and written information about the nature, purpose, possible risk and benefit of the study. Subjects must also be notified that they are free to discontinue from the study at any time. The subject should be given the opportunity to ask questions and allowed time to consider the information provided.

The subject's signed and dated informed consent must be obtained before conducting any study procedures.

The Principal Investigator must maintain the original, signed ICF. A copy of the signed ICF must be given to the subject.

14. APPENDICES

14.1. List of Abbreviations and Definitions of Terms

The following abbreviations and specialist terms are used in this study protocol.

Table 3: Abbreviations

Abbreviation	Explanation
ADL	Activities of daily living
AE	Adverse Events
ALC	Absolute lymphocyte count
ALT	Alanine aminotransferase
AST	aspartate aminotransferase
B-hCG	Beta human chorionic gonadotropin
CONSORT	Consolidated Standards of Reporting Trials
COVID-19	Coronavirus 2019
CRP	C-reactive protein
CTCAE	Common Terminology Criteria for Adverse Events, Version 5.0
DMC	Data monitoring committee
EC	Ethics Committee
ECG	Electrocardiogram
ECMO	Extracorporeal membrane oxygenation
e-CRF	Electronic case report form
ET	Early Termination
F	Fahrenheit
FA	Full analysis
FDA	Food and Drug Administration
FCBP	Female of child-bearing potential
FiO ₂	Fraction of inspired oxygen
FSH	Follicle stimulating hormone
G	Grade
ICF	Informed consent form
ICH	International Council for Harmonisation
ICU	Intensive Care Unit
IRT	Interactive Response Technology

Abbreviation	Explanation
JAK	Janus kinase
L/min	Liters per minute
MedDRA	Medical Dictionary for Regulatory Activities
miU	Milli international units
mL	Milliliters
PaO ₂	Partial pressure of oxygen in arterial blood
PI3K	Phosphoinositide 3 kinase
p.o.	By mouth
PP	Per protocol
PT	Preferred term
QD	Once daily
RBC	Red blood cells
Rbc/hpf	Red blood cells per high power field
RRT	Rapid response team
RT-PCR	Reverse transcriptase polymerase chain reaction
SAE	Serious adverse event
SARS-CoV-2	severe acute respiratory syndrome coronavirus 2
SAS	Statistical Analysis System
SOA	Schedule of Assessments
SOC	Standard of Care
SOC	System organ class
SOP	Standard operating procedures
TEAE	Treatment-emergent adverse events
ULN	upper limit of normal
VEGF	Vascular endothelial growth factor
WBC	White blood cells
WHO	World Health Organization

14.2. Ordinal Scale for Clinical Improvement

Ordinal Scale for Clinical Improvement

Patient State	Descriptor	Score
Uninfected	No clinical or virological evidence of infection	0
Ambulatory	No limitation of activities	1
	Limitation of activities	2
Hospitalized Mild disease	Hospitalized, no oxygen therapy	3
	Oxygen by mask or nasal prongs	4
Hospitalized Severe Disease	Non-invasive ventilation or high-flow oxygen	5
	Intubation and mechanical ventilation	6
	Ventilation + additional organ support – pressors, RRT, ECMO	7
Dead	Death	8

Source: https://www.who.int/blueprint/priority-diseases/key-action/COVID-19_Treatment_Trial_Design_Master_Protocol_synopsis_Final_18022020.pdf

## ABBREVIATIONS

AE	adverse event
BMI	body mass index
cm	centimeter
COVID-19	Coronavirus 2019
CRP	C-reactive protein
DMC	data monitoring committee
e-CRF	electronic case report form
ECG	electrocardiogram
ECMO	extracorporeal membrane oxygenation
FiO2	fraction of inspired oxygen
ICU	intensive care unit
IP	investigational product
kg	kilogram
kg/m 	kilogram per meter squared
L	liter
MAR	missing at random
max	maximum
MCAR	missing completely at random
MedDRA	Medical Dictionary for Regulatory Activities
mg	milligram
min	minimum
MMRM	Mixed-effects Model for Repeat Measures

MNAR	missing not at random
p.o.	By mouth
PaO2	partial pressure of arterial oxygen
PK	pharmacokinetics
PP	per protocol
QD	once daily
RRT	rapid response team
RT-PCR	reverse transcriptase polymerase chain reaction
SAE	Serious adverse event
SARS-CoV-2	severe acute respiratory syndrome coronavirus 2
SD	standard deviation
SOC	standard of care
SOC	System Organ Class
TEAE	treatment-emergent adverse event
VEGF-A	Vascular endothelial growth factor

## **1.0 INTRODUCTION OF THE STATISTICAL ANALYSIS PLAN**

The statistical analysis plan (SAP) is based on protocol STI-5656-2001 ‘A Phase 2, Randomized, Double-Blind, Placebo-Controlled Study of The Safety and Efficacy of Sti-5656 (Abivertinib Maleate) In Subjects Hospitalized Due to Covid-19’, V5.0 dated 07Dec2020. It details the methodology to be used in analyzing the data and outlines the specifications in the Tables, Figures and Listings (TFLs) for data to be included for executing the final statistical analyses for this study.

PK analysis is not included in this plan.

The analyses specified in this document supersede any high-level analysis plan described in the protocol.

## **2.0 INTRODUCTION TO THE STUDY**

### **2.1 Study Objectives**

#### **2.1.1 Primary Objective**

- To assess the efficacy of STI-5656 in subjects with severe COVID-19

#### **2.1.2 Secondary Objectives**

The secondary objectives of this study are:

- To assess the safety and tolerability of STI-5656 in subjects with severe COVID-19
- To assess pharmacokinetics (PK) in the study population.

### **2.2 Study Endpoints**

#### **2.2.1 Primary Endpoint**

The primary endpoint for the study is the:

- Proportion of subjects alive and free of respiratory failure at Day 28

#### **2.2.2 Secondary Endpoints**

- Types, frequencies, and severities of AEs and the relationships of AEs to IP; includes serious adverse events SAEs
- Proportion of subjects alive and free of respiratory failure at Day 60
- Change in clinical status (on a 0-8-point ordinal scale) of subject at Day 7, Day 14, and Day 28
- Proportion of subjects alive and discharged from ICU at Days 14 and 28
- Time from randomization to first occurrence of respiratory failure or death on study due to any cause up to Day 28
- Percent change from baseline in CRP at Days 3, 5, 7, 10, 14, 28
- Relative change from baseline in oxygenation index (PaO2/FiO2) up to Day 5

- All-cause mortality at Day 60 and Day 90
- Number of days alive and free of respiratory failure at Day 28
- Number of days with respiratory failure up to Day 28
- Number of days hospitalized up to Day 28
- Number of days in ICU (length of stay) up to Day 90
- Number of days alive outside of hospital up to Day 28
- Number of days alive outside of hospital up to Day 90
- To assess the pharmacokinetic profile in the study population

### 2.2.3 Exploratory Endpoints

- Change from baseline in absolute lymphocyte counts at Days 3, 5, 7, 10, 14, 28
- Change from baseline in ferritin at Days 3, 5, 7, 10, 14, 28
- Change from baseline in VEGF-A at Days 3, 5, 7, 10, 14, 28
- Change from baseline for inflammatory cytokines (IL-6, TNF- $\alpha$ , IFN $\gamma$ , IL1 $\beta$ , IL-7, IL-8, IL-10, IL-12, IL-17, IL-18, IP-10) at Days 3, 5, 7, 10, and 28

## 3.0 STUDY DESIGN

This is a Phase 2, randomized, double-blind, placebo-controlled, 2-arm multicenter study to assess the safety and efficacy of oral STI-5656 (or placebo) in the setting of current SOC in subjects with RT-PCR confirmed SARS-CoV-2 infection and COVID-19 pneumonia (documented radiographically) requiring hospitalization. Subjects must have oxygen saturation levels <94% on room air or subject requires supplemental oxygen.

Eighty (80) subjects meeting eligibility criteria will be randomized at a 1:1 ratio to one of two treatment arms in addition to SOC treatments:

- Arm 1: STI-5656
- Arm 2: Placebo

The STI-5656 dose is 100 mg p.o. QD administered up to 14 days or until hospital discharge if sooner.

Details of the study conduct, visit schedule and assessments are described in the protocol. The Schedule of Assessments is referenced in Appendix 1.

An independent data monitoring committee (DMC) is established to evaluate the safety data from the study to ensure the ongoing safety of the study subjects and make recommendations to the Sponsor concerning safety and trial conduct (please refer to the DMC charter for details). An unblinded independent statistician will be used to facilitate DMC support.

## 4.0 RANDOMIZATION AND BLINDING

This is a randomized and double-blinded study.

Subjects will be randomized using the IRT on Day 1 to either Treatment Arm 1 (STI-5656 plus SOC) or Treatment Arm 2 (placebo plus SOC) (1:1 ratio) using central integrated response technology (IRT). Subject study discontinuation or study completion should also be registered in the IRT. Sponsor, investigator and the CRO will be blinded throughout the study. The independent statistician who supports the DMC is unblinded.

Emergency unblinding may be requested by the Investigator at any time if needed to properly assess the safety of a patient. The request should be submitted to the CRO and Sponsor's medical monitor.

## **5.0 SAMPLE SIZE CONSIDERATIONS**

An evaluable sample size of 40 subjects per group will provide 80% power (alpha=0.05, 2-sided) to detect a difference between groups in the number of subjects alive and free of respiratory failure at Day 28. This assumes that 95.7% of subjects who received STI-5656 plus SOC and 70% of subjects who received placebo plus SOC only will be alive and free of respiratory failure at Day 28. This represents a treatment effect difference of approximately 26%.

## **6.0 ANALYSIS POPULATIONS**

### **6.1 Full Analysis Set (FAS)**

The full analysis set (FAS) includes all randomized patients. This is the intention to treat population. The FAS is based on the treatment allocated (as randomized). All efficacy endpoints will be analyzed using the FAS.

### **6.2 Safety Population**

The safety population includes all randomized patients who received any study drug. This set is based on the treatment received (as treated). Treatment compliance/administration and all clinical safety variables will be analyzed using the safety population.

### **6.3 Per Protocol (PP) Population**

The PP population is a subset of the FAS and excludes subjects with major protocol violations, entry criteria violations or missing visits. The PP population will be determined prior to the database lock and unblinding of the study. The PP population will be used for sensitivity analysis.

## **7.0 GENERAL STATISTICAL CONSIDERATION AND DEFINITIONS**

### **7.1 Baseline and Visit Windows**

Unless otherwise specified, baseline, which is defined as the last non missing assessment prior to the first dose of the study treatment, will be used in baseline and change from baseline analyses. Analyses will be performed according to the scheduled visits.

### **7.2 Summary Statistics**

Analysis will be summarized by treatment group of STI-5656 plus SOC or Placebo plus SOC, unless specified otherwise.

- Continuous endpoints will be summarized using descriptive statistics (number of participants, mean, standard deviation [SD], median, and maximum values) for each cohort. The summary statistic n will be the number of subjects with non-missing values. All means and medians will be reported to one more significant digit than the values being analyzed. Standard errors and standard deviations will be reported to two more significant digits than the values being analyzed. The minimum and maximum will be reported to the same number of significant digits as the values being analyzed.
- Categorical endpoints will be summarized as the number and percentage of participants per category for each cohort. Percentages will be out of the number of subjects in the population being reported, unless otherwise noted. All percentages will be rounded to one decimal point. The number and percentage of subjects will always be presented in the form XX (XX.X%) where the percentage is in parentheses. To ensure completeness, all summaries for categorical and discrete variables will include all categories, even if none of the subjects had a response in a particular category. Denominators for each analysis will be based on the population of interest (e.g., safety population; subjects with non-missing data).
- Subject listings of data will be presented for all enrolled subjects unless specified otherwise.

### 7.3 Missing or Incomplete Data

Subjects who are randomized to the study and discontinue before the end of the study will not be replaced. Missing values will not be imputed unless otherwise specified.

For success/failure endpoints, subjects who discontinue prior to the specified time point will be included in the analysis as treatment failures and censored at the last day of follow-up for the time-to-event analysis.

For all other endpoints, the mixed effect model repeat measurement (MMRM) analysis will be employed. The MMRM analysis only includes the available data. It has been demonstrated that the MMRM approach leads to estimators with comparatively small bias, and controls Type I error rates at a nominal level in the presence of missing completely at random (MCAR) or missing at random (MAR) and some possibility of missing not at random (MNAR) data (see <https://pubmed.ncbi.nlm.nih.gov/19212876/>).

### 7.4 Interim Analysis

A non-binding interim futility analysis will be performed after 40 subjects have reached the study primary endpoint. The analysis will be performed by an independent biostatistician who will have no contact with the study team.

This interim analysis will use non-binding futility boundaries. At 50% planned subjects (40 subjects out of 80 subjects total), futility interim will be performed. O'Brien-Fleming beta spending function will be used. Futility bound on Z scale is 0.537. The futility bound is crossed if an observed Z statistic is less than 0.537. Nominal beta is 0.296 with cumulative beta being 0.065 at the interim and 0.192 at the final analysis. The above interim planning was performed under 1-sided test setting using nQuery Version 8.6.1.0. Using 1-sided alpha of 0.025, with

continuity correction, sample size of 40 per group (80 total) have 80.8% power (beta 0.192) to detect the difference of 95.7% in active arm vs 70% in control arm.

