9.2. Sample Size Estimation

An evaluable sample size of 40 subjects per group will provide 80% power (alpha=0.05, 2-sided) to detect a difference between groups in the number of subjects alive and free of respiratory failure at Day 28. This assumes that 95.7% of subjects who received STI-5656 plus SOC and 70% of subjects who received placebo plus SOC only will be alive and free of respiratory failure at Day 28. This represents a treatment effect difference of approximately 26%.

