## **9.0 EFFICACY EVALUATION**

### **9.1 Primary Endpoint**

The primary efficacy endpoint is the proportion of subjects alive and free of respiratory failure at Day 28, where respiratory failure, is defined based on resource utilization of any of the following modalities:

- Noninvasive positive pressure ventilation or continuous positive airway pressure
- Endotracheal intubation and mechanical ventilation
- Oxygen delivered by high-flow nasal cannula (heated, humidified, oxygen delivered via reinforced nasal cannula at flow rates  $>20$  L/min with fraction of delivered oxygen  $\geq 0.5$ )
- Extracorporeal membrane oxygenation

The number and percentage of subjects will be presented by treatment group using FAS population. Primary analysis to evaluate the differences between groups will utilize a

generalized linear mixed model, assuming a binomial distribution and a logit link. The model will include group as a fixed effect. Subjects who discontinue the study prior to Day 28 will be considered treatment failures.

Sensitivity analyses may be performed using PP population.

After 40 subjects have been enrolled and completed Day 28, an interim futility analysis will be performed to examine the proportion of subjects alive and free of respiratory failure at Day 28. The interim analysis is a non-binding analysis. See Section 7.4 for details.

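### The 80% / 80.8% power is for a continuity-corrected two-proportion test, not for the logit model named as primary analysis, whose test statistic and zero-failure rule are unstated

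*SAP*

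**What the plan says.** **Sizing.** SAP 5.0 states: "An evaluable sample size of 40 subjects per group will provide 80% power (alpha=0.05, 2-sided) to detect a difference between groups". It gives the rates as follows: "This assumes that 95.7% of subjects who received STI-5656 plus SOC and 70% of subjects who received placebo plus SOC only" will meet the endpoint. Protocol 9.2 uses the same inputs. Neither section names a test.

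**Interim planning.** SAP 7.4 does name its method. It works one-sided ("Using 1-sided alpha of 0.025, with" the correction) and reports "continuity correction, sample size of 40 per group (80 total) have 80.8% power (beta 0.192"). It spends that beta with an O'Brien-Fleming-type function: 0.065 at the interim, futility bound Z = 0.537, nominal beta 0.296. The bound is non-binding. The Z statistic to be compared with 0.537 is not defined.

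**Primary analysis.** SAP 9.1 specifies a "generalized linear mixed model, assuming a binomial distribution and a logit link. The model will include group as a fixed effect". Protocol 9.4.3 agrees. Neither says whether the group effect is tested by Wald, score or likelihood ratio. Neither says what happens if an arm has no failures. Subjects who leave before Day 28 count as failures, but no discontinuation rate is given.

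**The concern.** The power was computed for one statistic and the trial will be judged by another. In many trials this would be a detail. Here the planned active rate is close to 100% with only 40 subjects, so the usual large-sample tests of a logit model differ clearly from one another and from the corrected test used for sizing.

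Two things are at stake. First, the printed power tells a reader how much weight a non-significant result carries, and the true figure could be well above or well below it. Second, the open choice could decide the result. If every active subject succeeds, the estimated log odds ratio is infinite, its Wald standard error explodes, and a plain Wald test is non-significant whatever the control arm does. The best possible outcome in the active arm would then be reported as no evidence of effect.

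**Working it through.** **Inputs.** p1 = 0.957 and p2 = 0.70 (SAP 5.0); n = 40 per arm; two-sided 0.05 (SAP 5.0), equivalent to one-sided 0.025 (SAP 7.4), so the critical value is 1.96 in both. Group is the only model term and no random effect is named, so I treat the model as ordinary logistic regression on a 2 x 2 table.

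**1. Reproduce the printed power.** d = 0.957 - 0.70 = 0.257; pooled rate = 0.8285.

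- SE under the null = sqrt(2 x 0.8285 x 0.1715 / 40) = 0.0843.
- SE under the alternative = sqrt((0.957 x 0.043 + 0.70 x 0.30) / 40) = 0.0792.
- With the correction 1/n = 0.025: (0.257 - 0.025 - 1.96 x 0.0843) / 0.0792 = 0.843, power 80.0%.
- Without the correction: (0.257 - 1.96 x 0.0843) / 0.0792 = 1.158, power 87.7%. The unpooled version gives 90.0%.

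The 80% therefore matches the corrected formula and not the uncorrected ones. The unpooled corrected formula gives 83.3%, or 81.4% after the loss from futility stopping, so the corrected versions bracket 80.8%.

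**2. Check the interim figures.** Spending a total beta of 0.192 at half information gives 2 x [1 - Phi(1.305 / sqrt(0.5))] = 0.065. The nominal beta is 1 - Phi(0.537) = 0.296. The bound and interim beta imply a final drift of (0.537 + 1.514) x sqrt(2) = 2.90, and then P(Z1 > 0.537 and Z2 > 1.96) = 0.808. SAP 7.4 is internally consistent.

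**3. Exact power of the written model.** I enumerated all 41 x 41 outcomes of Binomial(40, 0.957) and Binomial(40, 0.70), applied each two-sided 5% test and summed the probabilities of rejection. No discontinuations and no futility stop are assumed.

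| Test | Exact power |
|---|---|
| Score (uncorrected Pearson chi-square) | 91.5% |
| Likelihood ratio | 91.5% |
| Wald, score fallback for a zero cell | 87.7% |
| Wald, exact (Fisher) fallback for a zero cell | 87.6% |
| Wald, 0.5 added to each cell | 86.8% |
| Wald, no fallback | 70.5% |
| *For comparison:* Fisher exact | 85.5% |
| *For comparison:* continuity-corrected chi-square | 82.3% |

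If the trial stops whenever an uncorrected pooled Z at 20 versus 20 falls below 0.537, the score test has 90.2% and plain Wald 69.5%.

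**4. Where the low figure comes from.** P(no failures among 40 active subjects) = 0.957^40 = 17.2%. Plain Wald loses almost exactly that: 87.7% - 70.5% = 17.2 points. Against a 70% control rate its power peaks at 72.2% (active rate about 94.5%) and never reaches 80%.

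**5. Single outcomes.** For 40/40 versus 28/40 the score Z is 0.30 / sqrt(2 x 0.85 x 0.15 / 40) = 3.76, p = 0.0002, while plain Wald is non-significant. For 39/40 versus 33/40, with no empty cell, the score test gives p = 0.025 and Wald p = 0.054.

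**6. Discontinuations counted as failures.** No rate is given, so I assume equal dropout in both arms, 40 randomized per arm, and 95.7% and 70% as rates before dropout. At 5% the rates become 0.957 x 0.95 = 0.909 and 0.70 x 0.95 = 0.665.

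| Dropout | Score | Wald with score fallback | Plain Wald |
|---|---|---|---|
| 0% | 91.5% | 87.7% | 70.5% |
| 2.5% | 85.4% | 82.1% | 75.9% |
| 5% | 79.3% | 76.7% | 74.5% |

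**The case against.** The strongest reply is that nothing was miscalculated. SAP 7.4 states its method and its numbers reproduce. Sizing with a continuity correction is a common small-sample allowance, and under most choices of test the trial has more power than printed. That stands: this is a mismatch of specification, not an arithmetic error.

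A reader might infer that the stated power is wrong however the plan is read. The documents do not support that. The figure is right for the test it names. Fisher's test, which is the exact conditional test of a group-only logit model, has 85.5%, within 5 points of 80.8%. With 5% discontinuation counted as failure, the score test falls to 79.3%, close to the printed 80%.

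A reader might also object to the Protocol's sentence "This represents a treatment effect difference of approximately 26" percent as a wrong detectable difference. It is not one: it is 95.7 minus 70, an assumed effect, correctly subtracted.

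Finally, one might infer that the futility bound is wrong because it spends the beta of a different test. That is not shown. The interim Z is undefined, so it could be the corrected statistic, and the bound is non-binding.

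The reply leaves one thing open. The SAP neither selects nor excludes plain Wald, and under that choice the trial has less power than stated.

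**Conclusion.** The point holds as a mismatch between the power calculation and the primary analysis. At the planned rates with no discontinuations, the usual tests of the written model have exact power of 91.5%, about 87-88% or 70.5%, against a printed 80% / 80.8%. The gap from 80.8% runs from about +6 to +11 points, or is about -10 points, depending on a choice that the SAP leaves open.

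These figures assume 40 evaluable subjects per arm, an ordinary logistic fit and no dropout. The 70.5% further assumes that an arm with no failures is counted as non-significant. That SAP 5.0 and Protocol 9.2 used the corrected test is inferred from reproducing their 80%; only SAP 7.4 says so. The finding does not show that the trial is underpowered, and it does not call for more patients.

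**What to change.** - **SAP 9.1 and Protocol 9.4.3:** name one test of the group effect that stays valid when an arm has no failures. Examples are the score test, which equals the uncorrected Pearson chi-square, or Wald with a prespecified exact or score fallback for a zero cell.
- **SAP 5.0, SAP 7.4 and Protocol 9.2:** restate the power for that test, and say whether 95.7% and 70% already count discontinuations as failures. If they do not, print a range such as the one in step 6 of the working rather than a single figure.
- **SAP 7.4:** define the Z compared with 0.537 and recheck the beta spending for consistency with the chosen test.

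**Cost.** Wording and one planning re-run; no added patients or data. There is a small price in type I error. Enumerated over common rates from 0.50 to 0.985, the exact level reaches about 5.9% for the score test (near a common rate of 91%) and about 5.7% for Wald with an exact or score fallback; the continuity-corrected test stays at or below 3.3%. Likelihood ratio is the weaker choice: it reaches 9.1% near a common rate of 95%, and used only as the zero-cell fallback it still gives 8.5%.
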